Immuno-modulation is mostly achieved by preventing egression of lymphocytes from lymphoid organs, and the modulation of cytokine expression, including microglia⁵. For T lymphocytes, it was shown that S1PR modulators prevent the infiltration of CD8+ memory cells in the central nervous system (CNS). This property could be key for AD since, very recently, the group of Wyss-Coray showed that CD8+ T cells likely play a critical role in the adaptive immune response in the CNS of AD patients^{17,42}. On the other hand, the molecular mechanisms for neuroprotection are currently poorly understood. Nonetheless, both fingolimod and Siponimod lower the rate of brain atrophy in remitting relapsing MS (RRMS)⁷. Very interestingly, Siponimod was found to reduce brain atrophy at later stages of MS called secondary progressive MS (SPMS), making it the first drug with a demonstrated neuroprotective effect in SPMS¹². More precisely, at month 12 the percentage of total brain volume change from baseline adjusted mean were -0.28% and -0.46% ($p < 0.0001$) in Siponimod vs placebo-treated SPMS subjects, respectively²⁵.

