12. STATISTICAL CONSIDERATIONS

STATISTICAL HYPOTHESES

- Primary and Exploratory Efficacy Endpoint(s):

The null hypothesis for the primary efficacy endpoint is that biomarker measures (primary endpoint: vMRI; tertiary and exploratory endpoints: CSF biomarkers, blood inflammatory markers, saliva amyloid beta levels) will be the same in Siponimod- vs. placebo-treated study subjects after 12 months (end of dosing).

The alternative hypothesis is that Siponimod will improve biomarker measures at the same time point.

- Secondary Efficacy Endpoint(s):

The null hypothesis for the secondary efficacy endpoint is that cognitive measures (ADCOMS) will be the same in Siponimod - vs. placebo-treated study subjects after 12 (end of dosing) and 18 months (6 months follow up).

The alternative hypothesis is that Siponimod will improve cognitive measures at the same time points.

SAMPLE SIZE DETERMINATION

Mild AD subjects will receive an escalating dose of Siponimod up to 1 mg/day (N=70) or placebo (N=35) for 12 months (Table 2). We conducted a power analysis for sample size determination using the reported data from brain volume changes in SPMS subjects treated for at least 12 months with Siponimod or placebo²⁵. We wished to fit a repeated measures ANOVA model with two treatment levels in drug vs. placebo, and 4-time measures to receiving the drug (i.e. vMRI at baseline, 6, 12, and 18 months). We defined $Y_{ij} = \mu + \alpha_i + \tau_j + (\alpha\tau)_{ij} + \varepsilon_{ijk}$, where Y_{ijk} denotes the measure on brain atrophy, α_i denotes the treatment effect $i = 1, 2$; τ_j denotes the time effect at time $j=1, 2, 3, 4$; $k = 1, n$; $(\alpha\tau)_{ij}$ is the interaction between time and treatment; and ε_{ijk} is the error term²¹. We study the effect of the drug on brain atrophy. The between-subject factor in our model is treatment, with two levels (study drug and placebo), and we allocate each treatment in the ratio 2:1. The within-subject factor is time, with four levels (0, 6, 12, and 18 months). The number of patients needed is determined to achieve a power of 0.90 at significance level $\alpha = 0.05$ for the test of the interaction between time and treatment, where the contrast over time contains all pairwise comparisons. We also intend to generate a plot of power versus sample size that covers the power range of 0.05 to 0.90.

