The default Hotelling-Lawley F test is appropriate for this study, especially because it is the same as the Wald test in PROC MIXED with the DDFM=KR Kenward-Roger degrees-of-freedom method and an unstructured covariance model. We conjecture that the mean measure of brain atrophy will decrease by 20-30% (GLMPOWER Procedure SAS/STAT User's Guide 9.2). To characterize the variability, we specify a set of parameters that defines the entire covariance matrix of the residuals. We conjecture that the error standard deviation is the same at all four time points, with a value approximately 4-11, and we account for uncertainty by including both the lower and upper ends of this range in the sample size analysis. The power analysis is given in Table 1. A power of 90% is obtained with 90-95 subjects to determine a difference in brain atrophy over placebo. To account for a possible ~10% attrition rate, we will use 105 subjects in total.

Table 4: Power Analysis Versus Sample Size.

Index	Transformation	Effect	Actual Power	N Total
1	Time	Time	0.903	90
2	Mean (Dep)	Treatment	0.906	94

We chose to study mild AD subjects for the major reason that these patients do suffer continuous but limited/slow brain atrophy, which is measurable by vMRI²², vs. mild cognitive impairment patients (MCI), whose brain atrophy may not progress enough on an annual basis for robust quantification. Furthermore, the functional disabilities in mild AD patients are not too pronounced yet vs. moderate and severe AD. Thus, if Siponimod is able to slow down brain atrophy, mild AD subjects will likely benefit the most by, hopefully, also slowing down functional decline.

POPULATIONS FOR ANALYSES

All subjects receiving at least 1 dose of study drug will be included in the safety analyses. For efficacy analyses, subjects will be included only if they reach Visit 12 (Week 8) of the dosing period (i.e., patients withdrawn before Visit 12 and replaced will not be included in this efficacy analysis). Patients withdrawing or withdrawn from the study before Visit 12 are unlikely to demonstrate a change in the biomarkers investigated here (cognitive performance) given the effects of Siponimod in the CNS take several weeks to be measurable.

STATISTICAL ANALYSES

GENERAL APPROACH

All intra and inter-subject outcome measures collected during our study will be sent to [name] at Arizona State University for statistical processing.

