The data will be summarized using professional standards. The distributions of patients completing each study visit and the reason for early terminations will be tabulated for each treatment group. The duration of double-blind treatment within each treatment group and compliance rates will be summarized by descriptive statistics (mean, standard error, standard deviation, median, minimum, maximum and sample size) for days of treatment and for total days of exposure and by the distributions of patients exposed to various durations of treatment categories. Demographic and baseline characteristics will be summarized by descriptive statistics for all patients in each treatment group.

Volumetric MRI data measures will be computed to determine eventual brain volume changes between pre- and post-treatment, which will validate or refute our central hypothesis. Data from Aims 2-3 will also be used in correlational analyses for blood vs. AD central markers to investigate whether minimally invasive tests that use peripheral markers could be used as proxies to track drug performance. We wish to fit a repeated measures ANOVA model with two treatment levels (drug and placebo) and 13 time measures (for blood markers). We define $Y_{ij} = \mu + \alpha_i + \tau_j + \varepsilon_{ijk}$, where Y_{ij} denotes the measure on siponimod, α_i denotes the treatment effect $i=1,2$, τ_j denotes the random effect at subject $j=1, 2, \dots, 70$, $k=1, \dots, 13$ and ε_{ijk} is the error term. We assume that the random effect is distributed with mean zero and σ^2 . Paired data tests will be used to assess eventual biomarker changes between pre- and post-dosing datasets. Correlational statistics and linear regressions will be employed to determine possible dose-response for siponimod on the biomarkers investigated. If siponimod has an effect on inflammatory and AD biomarkers (either in blood, or in CSF), the current study should demonstrate an amelioration of these biomarker profiles. Also, we will use the results of cognitive tests to calculate the average conversion rate, continuous variables, and time to event analysis in our two groups.

Missing data will not be imputed, and all summary statistics will be reported based upon observed data. For limited analyses where formal inferential analyses are specified, rank-based methods will be used to incorporate subjects missing follow-up assessments.

ANALYSIS OF THE PRIMARY EFFICACY ENDPOINT(S)

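### The only stated rule for missing follow-up in formal inference is rank-based: it needs an assigned rank despite the bar on imputation, yields no atrophy rate, and is not the test that was powered

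*Protocol*

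**What the plan says.** All of this is in section 12 of the protocol.

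- **Missing data (General Approach).** "Missing data will not be imputed, and all summary statistics will be reported based upon observed data". The next sentence, limited to those analyses where formal inference is specified, says that "rank-based methods will be used to incorporate subjects missing follow-up assessments". Neither the rank nor the analyses concerned are named. The same section plans a repeated-measures ANOVA for blood markers, paired tests and linear regressions.
- **Power (Sample Size Determination).** The number of subjects is set for 0.90 power at alpha 0.05 "for the test of the interaction between time and treatment, where the contrast over time contains all pairwise comparisons", using the Hotelling-Lawley F test from a GLMPOWER calculation. That test is preferred partly because "it is the same as the Wald test in PROC MIXED with the DDFM=KR Kenward-Roger degrees-of-freedom method and an unstructured covariance model". The result is 90 to 95 subjects, raised to 105 for about 10% attrition.
- **Endpoint analyses.** For vMRI, which is to give the annual rate of brain atrophy, and for ADCOMS, the text promises comparisons of change from baseline and names no test.
- **Hypotheses.** vMRI is to be compared at 12 months, ADCOMS at 12 and 18 months.
- **Efficacy population.** Only subjects who reach Visit 12, labelled there as Week 8, are included.

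**The concern.** Because the endpoint sections name no test, the rank sentence is the only statement of how missing follow-up enters formal inference. It departs from the rest of the plan in three ways.

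1. Ranking a subject whose value is absent means giving that subject an outcome, which sits badly with a rule of no imputation.
2. A rank comparison with assigned ranks gives a p-value but no annual atrophy rate, and the rate is the quantity that the secondary objective asks for.
3. It is not the parametric test from which the 90% power was obtained.

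At stake is whether the stated power applies to the analysis that is run. If missingness differs by arm, it is also whether a tolerability difference enters the efficacy comparison through the ranks.

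**Working it through.** **1. The plan's own figure.** 94 / (1 − 0.10) = 104.4, which rounds up to 105. This reproduces. The inflation treats lost subjects as contributing nothing. That fits an analysis of observed values and not one that ranks those subjects in.

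**2. What cannot be reproduced.** The 90 and 94 in Table 4 need absolute means, units and within-subject correlations. The protocol gives only a conjectured 20–30% decrease and an "error standard deviation is the same at all four time points, with a value approximately 4-11", without units or correlations. Table 4 labels its rows time and treatment, while the text speaks of the interaction. Either way the powered test is a parametric F test, so the mismatch with a rank method does not turn on this.

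**3. A working effect size (assumption).** For a simple two-group comparison at 2:1, two-sided alpha 0.05 and 90% power, the detectable standardised difference is d = (1.960 + 1.282) × √(3/N + 3/(2N)).

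- N = 94: d = 0.71
- N = 105: d = 0.67

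The midpoint, 0.69, is used below. It is not a protocol figure.

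**4. Closed-form check on observed data.** With 10% missing in both arms, 63 and 31.5 subjects remain. SE = √(1/63 + 1/31.5) = 0.218 and 0.69/0.218 = 3.16. Power = Φ(3.16 − 1.96) = 0.88.

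**5. Simulation.** One change score per subject, 70 versus 35, missingness unrelated to the value. A t test on observed data is compared with a Mann-Whitney test in which missing subjects receive either the worst or the middle rank. Figures are rounded; repeat runs gave worst-rank power of 0.38 to 0.39 in the second row.

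| Missing, drug / placebo | t test, observed data | Middle rank | Worst rank |
|---|---|---|---|
| 10% / 10%, power | 0.88 | 0.85 | 0.73 |
| 15% / 5%, power | 0.88 | 0.86 | 0.39 |
| 20% / 5%, power | 0.87 | 0.85 | 0.19 |

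Under no effect with 15% / 5% missing, worst rank rejects in about 12–13% of trials against siponimod and about 0.2–0.3% in its favour. With middle rank the total stays near 5%.

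With an effect of 0.71 SD and 10% missing in both arms, power is 0.76 (worst rank), 0.88 (middle rank) and 0.90 (observed data), so the pattern does not depend on the exact effect.

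**6. Whom the rule could reach.** In Table 1, Visit 12 is Day 336 (Week 48), and Week 8 is Visit 6. If the efficacy population means Week 48, earlier dropouts are excluded and only later losses could be ranked. If it means Week 8, most dropouts could be. The protocol supports both readings.

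**The case against.** The strongest reply is that the two missing-data sentences are a general rule and a limited exception. On that reading there is no flat contradiction, and which analyses are meant and which rank is assigned could sit in a statistical analysis plan that is not shown. This is fair: the two sentences are in tension, and the absence of the rank is not by itself a finding. It does not remove the conflict between the rank rule and the powered test, because both are stated in the protocol.

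A reader might also infer more than the text supports:

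- **That the sample size rests on a likelihood-based mixed model.** It rests on a Hotelling-Lawley F test. PROC MIXED is cited only as giving the same test, and attrition is handled by inflating N.
- **That subjects with no follow-up at all are ranked.** The wording is about missing follow-up assessments, which includes subjects with partial data.
- **That worst rank is planned.** It appears nowhere. With middle rank the loss is small.
- **That unequal dropout would produce false claims of benefit.** If more values are missing on drug, worst rank pushes rejections against siponimod. False claims in its favour fall below 2.5%.
- **That the toxicity rules will empty the drug arm of data.** Section 10 has subjects withdrawn for toxicity undergo the Week 52 assessments, which include vMRI and cognition, and asks them to complete Weeks 56 and 78. Section 9 asks other discontinuers to return for Weeks 52 and 78. Unequal missingness remains plausible: Table 2 shows transaminase increase in 11% versus 3% and bradycardia in 6% versus 3%, at 2 mg in MS patients. Those are reaction rates, not dropout rates.

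**Conclusion.** The point holds as a mismatch that should be resolved before the data are unblinded. As written, formal inference with missing follow-up uses a method that requires assigned ranks, does not estimate the atrophy rate and is not the test behind the stated 90% power.

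The size of the effect depends on an unstated choice. With equal 10% missingness the power cost is about 3 points with middle rank (0.88 to 0.85) and 15 points with worst rank (0.88 to 0.73). Only worst rank combined with unequal missingness is severe. These figures rest on an assumed 0.69 SD effect, a single change score in place of the four-time interaction test, and missingness applied to all 70 and 35 subjects before any restriction to those who reach Visit 12. They show how much the rank rule matters and do not predict this trial's power. The total of 105 is not shown to be wrong.

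**What to change.** In section 12:

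1. Name the mixed model already cited in Sample Size Determination as the analysis of vMRI and ADCOMS: unstructured covariance, Kenward-Roger degrees of freedom, all available post-baseline values, no imputation. Report the time-by-treatment test that the text says was powered, plus the contrasts that match the hypotheses: month 12 for vMRI, months 12 and 18 for ADCOMS. A month-12 contrast alone would not be the powered test and would omit the 18-month ADCOMS hypothesis.
2. Delete the rank sentence, or keep it as a sensitivity analysis with the assigned rank defined.
3. Reconcile the efficacy population with Table 1 (Visit 12 against Week 8) and word it so that subjects with partial post-baseline data are included. Otherwise the model cannot use the data that make it preferable.

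The cost is a short rewrite of section 12, including the efficacy population, so more than one sentence. It adds no visits and no subjects.
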